10.1.2 ANALYSIS OF THE PRIMARY EFFICACY ENDPOINT(S)

A safety review of treatment Groups 1 and 2will be performed. Safety endpoints will be monitored at each study visit and at each monitoring visit.

Study Stopping Criteria

- local intolerance of the administered Kineret or any sign of allergic response.
- development of signs and symptoms before the second time point preventing the second administration of the study drug.
- Any patient reported SAE after the first or second administration of the study drug.
- Diagnosis with any condition as outlined in the exclusion criteria during the course of the initial 2 weeks of study enrollment.

10.1.3 ANALYSIS OF THE SECONDARY ENDPOINT(S)

Not applicable

10.2 MEASURES TO MINIMIZE BIAS

10.2.1 ENROLLMENT/ RANDOMIZATION/ MASKING PROCEDURES

Randomization: Following informed consent and after successfully being screened into the study, subjects will be randomized to one of three treatment groups.

- **Group 1** will receive intra-articular injection of Anakinra (Kineret®, IL-1ra; 150mg) 1-28 days after ACL injury.
- **Group 2** will receive intra-articular injection of saline placebo 1-28 days after ACL injury.

Blinding: To ensure triple-blindness, an uninvolved third party will generate the allocation sequence of the intervention and provide this to the principal investigator. Allocation of drug or placebo will be by permutated random block size, ensuring that approximately equal numbers of subjects will be treated with drug or placebo in the unlikely event that the study will need to be terminated prematurely.

If subject discontinues the study for any reason prior to 3-month visit, then the collected data will be evaluated but not included in the analysis and a replacement subject will be enrolled in the study.

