4 STUDY DESIGN AND ENDPOINTS

4.1 DESCRIPTION OF THE STUDY DESIGN

This is a phase 2, prospective, randomized, triple-blinded, placebo-controlled study of IL-1RA treatment in patients with acute ACL tear and painful effusions. The study population will include up to 40 participants within 28 days of injury. The study is open to male and female participants who are between the ages of 14 and 40, who have ACL tears. Once enrolled will be randomized into 2 groups (20 subjects per group).

- **Group 1** will receive intra-articular injection of Anakinra (Kineret®, IL-1ra; 150mg) 1-28 days after ACL injury.
- **Group 2** will receive intra-articular injection of saline placebo 1-28 days after ACL injury.

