6 STUDY AGENT

6.1 STUDY AGENT(S) AND CONTROL DESCRIPTION

6.1.1 ACQUISITION

Unblinded study drug will be shipped from the manufacturer Swedish Orphan Biovitrum (Sobi) directly to the site research pharmacist, after all required regulatory and legal documents have been received by the Sponsor.

Replacement Procedures For Investigational Medicinal Product: Resupply shipments or replacement of study drug will be provided by Sobi after consultation with [name].

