6.1.4 PREPARATION

The study drug will be kept in a temperature controlled environment according to the manufacturer's recommendations

Under aseptic clean conditions, a total of 200 mg (1.34 mL) of Kineret® (concentration 100mg/0.67ml) will be injected from 2 sterile original prefilled 100 mg syringes of Kineret into a sterile vial. A sterile graduated 5 mL syringe will then be used to draw 150 mg (1 mL) of Kineret for intraarticular injection into the knee. The medication must be transferred from the original prefilled Kineret syringes as the needles are intended for subcutaneous delivery and are not adequate for intra-articular knee injection. No dilution of the medication will be performed.

For the placebo we will utilize 1 mL of 0.9%NACL sterile saline solution drawn up in the same type of syringe as for the Kineret administration in order to maintain double blinding of the study investigator and patients.

The number of study syringes prepared by the designated research personnel or research pharmacist, per day, will depend on the number of potential enrollees or return patients requiring Kineret® injections that day.

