The power calculations include several caveats. First, for purposes of power calculation, we did not assume a full repeated measures analysis, but instead analyzed at a single time point (oneyear follow-up). Second, we note that in trials such as this, the power of a non-parametric analysis is never much lower than its parametric analog (the "asymptotic relative efficiency" of the Wilcoxon test is at least 0.95), leading us to conclude that our parametrically based power calculations should apply with equal force to a non-parametric analysis.

Statistical analyses - Results from a sample of this size may not be normally distributed. Therefore, non-parametric statistical measures may be used. Primary outcome measures evaluating for change in KOOS will be assessed at multiple points and will be analyzed for change between groups using Friedman two-way ANOVA for repeated measures. Synovial fluid analyses comparing the three groups at five time points will be analyzed using the Wilcoxon Signed Rank Sum Test with Hochberg corrections for multiple time points. Alternatively, if results are normally distributed or can be transformed (e.g., by log transformation) to meet the criteria for normality for parametric analysis, then repeated measures ANOVA will be utilized comparing treatment groups. P-values of less than or equal to 0.05 will be considered statistically significant.

Predicted Results: IL-1ra, while potent, has had mixed results in the treatment of established OA, possibly due to it's short half-life in vivo. In this trial, we expect that an early intervention with IL-1ra will effectively block the deleterious cascade of joint degradation events after joint injury. We expect a significant effect of IL-1ra on post-injury pain and concomitantly an increase in patient-reported outcomes due to the improved early function

Minimization of bias: Due to the randomized study design and the blinding of the investigator and patient to the drug used, we hope to eliminate any investigator or subject bias. Using broad and previously established enrollment criteria we hope to reduce selection bias to a minimum while protecting potentially vulnerable individuals through the exclusion criteria. Procedural bias and measurement bias will be reduced by the multicenter design and the blinded data analysis.

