10.2.3 BREAKING THE STUDY BLIND/PARTICIPANT CODE

Breaking the randomization code will be performed by the Principal Investigator and will occur if it is necessary for the care of the subjects. For example, if an AE or SAE occurs with the a subject and knowledge of the drug randomization would be important for clinical care or to determine appropriate treatment, then the principal investigator will break the code and the subject will be withdrawn from the study.

Unblinding of a subject(s) dosing will be documented and will include an explanation of why the study medication was unblinded.

Following data lock, subject dosing information can be unblinded and the unblinded information can be sent to the study participants at the discretion of the principal investigator.

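### Section 10.2.1 gives the allocation sequence to the principal investigator with no stated sealing, masking or access limit, which conflicts with the stated investigator blinding and with the code-break rule in 10.2.3

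*Combined protocol and SAP*

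**What the plan says.** Section 10.2.1 gives triple-blinding as its aim and then says that "an uninvolved third party will generate the allocation sequence of the intervention and provide this to the principal investigator". Allocation is by permuted blocks. In the available text this is the only sentence on who receives the list.

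The blinding claims are these:

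- Section 4.1: "This is a phase 2, prospective, randomized, triple-blinded, placebo-controlled study of IL-1RA treatment". The title in the Protocol Summary also calls the trial triple-blinded.
- Section 6.1.4: the placebo is drawn up in the same type of syringe "in order to maintain double blinding of the study investigator and patients".
- Section 10.1.1, on minimization of bias: the plan relies on randomization and on "the blinding of the investigator and patient to the drug used".

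Section 10.2.3 governs unblinding. "Breaking the randomization code will be performed by the Principal Investigator and will occur if it is necessary for the care of the subjects". If knowledge of the arm matters for care, "then the principal investigator will break the code and the subject will be withdrawn from the study". Each unblinding is documented and explained. "Following data lock, subject dosing information can be unblinded".

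On drug handling, 6.1.1 says that "Unblinded study drug will be shipped from the manufacturer" to the site research pharmacist, while 6.1.3 sends it to designated research staff. Section 6.1.4 lets either designated personnel or the research pharmacist prepare syringes. Sections 6.1.3 and 6.1.5 match each syringe to the patient ID. Section 6.2 makes the sponsor/investigator responsible for supervising dispensing and accounting, with forms that account for drug subject by subject.

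**The concern.** A person who can read the allocation sequence is not blind to it. Section 10.2.1 therefore works against its own stated aim. Staff who carried it out literally would hand the PI every past and future assignment.

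What is at stake is the protection that the plan itself names against investigator bias in 10.1.1. A PI who knows the arm could be influenced when approving restricted co-medication or withdrawing a patient. The second matters more than usual here, because 5.4.2, 6.1.9 and 10.2.1 all say that a patient who discontinues before the 3-month visit is left out of the analysis and replaced. Knowledge of the arm could then affect which patients are analysed, in a trial with at most 20 per group. Section 10.2.2 marks evaluation of blinding as not applicable, so the plan has no check that would reveal a failure.

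**Working it through.** No figure in the documents depends on this point, so there is nothing to recompute. The check is to set the sections side by side.

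1. **Who holds the list, and in what form.** Section 10.2.1 names the PI and says that the sequence itself is provided. The sections on supply, storage, preparation, dosing, accountability, masking and code breaks (6.1.1 to 6.1.5, 6.2, 10.2.1 to 10.2.3) state no sealing, masked arm labels, access limit or other holder of the list.

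2. **Compatibility with investigator blinding.** Sections 6.1.4 and 10.1.1 say that the investigator is blinded, and 4.1 says that the trial is triple-blinded. These hold together with 10.2.1 only if the PI cannot read what the PI is given. That condition is not stated.

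3. **Compatibility with the code break.** Section 10.2.3 presupposes that the PI does not know the arm until a care need arises. With a readable list there is no code left to break, and the duty to document each unblinding loses its meaning. Sections 10.2.1 and 10.2.3 are consistent only with a safeguard that neither describes.

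4. **What ID-matched syringes achieve.** They mask the person giving the injection. They do not limit who may read the list.

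5. **Where knowledge of the arm could act.**
   - *Primary endpoint (4.2.1).* KOOS-Symptoms is self-reported (7.1.1) and self-administered (10.1.1). The PI does not score it, so the direct risk is limited.
   - *Co-medication (7.6).* Immunosuppressants including corticosteroids, non-steroidal anti-inflammatory drugs and drugs affecting clotting are barred unless the PI approves them. This is a clear PI decision that knowledge of the arm could influence.
   - *Withdrawal (5.4.2, 10.2.3).* The investigator may withdraw a patient for safety or scientific reasons, and a code break leads to withdrawal. If this happens before the 3-month visit, the patient leaves the analysis and is replaced. This is the most direct route to the efficacy result. The code break is not an independent route: a PI with a readable list gains no new information from it, and it matters here because withdrawal follows.
   - *Adverse events (8.2.3, 8.4.1).* The PI assesses occurrence and judges expectedness. This is a lesser route. Section 8.3 requires every event to be documented whatever its relationship, 8.2.2 says that relationship does not decide what is reported, and expectedness is judged against existing risk information. Severity and causality are assigned to the clinician (8.2.1, 8.2.2), not specifically to the PI.

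6. **Who could hold the list instead.** The research pharmacist already receives unblinded drug under 6.1.1. Sections 6.1.1, 6.1.3 and 6.1.4 do not agree on whether that person or other designated staff receive the drug and prepare the syringes. If the per-subject records in 6.2 identify the product, they are a second way for the supervising sponsor/investigator to learn the arm.

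**The case against.** The strongest reply is that the PI was always meant to hold a coded or sealed list for emergencies. Section 10.2.3 speaks of a randomization code that has to be broken, 10.2.1 gives triple-blinding as its purpose, and syringes are tied to patient IDs. Some pages are missing from the text available for review, and the manual of procedures mentioned in 14.3 is not supplied. On this view the defect is a missing sentence.

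Part of this stands. A concealed list is a plausible intention, and the most that can be said about safeguards is that the available text states none. It does not remove the conflict: 10.2.1 gives an instruction, and a safeguard described elsewhere would still leave that instruction wrong as worded.

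It is also fair that the harm is indirect. The adverse-event duties are constrained, 5.4.2 names the investigator rather than the PI, and a count of decision points would not measure bias.

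A reader might infer more than the documents support:

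- *That the PI was in fact unblinded.* The text shows a conflicting instruction, not what was done.
- *That enrolment was open to selection.* Several surgeons recruit (5.3), and nothing shows that they would see the list.
- *That patients, the MRI laboratory or the biomarker laboratory are unblinded.* Nothing in 10.2.1 gives any of them the sequence.

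**Conclusion.** The point holds as a conflict within the protocol that should be fixed. Section 10.2.1, as worded, gives the PI a readable allocation sequence. That cannot be squared with the investigator blinding in 6.1.4 and 10.1.1, the triple-blind design in 4.1, or the code-break rule in 10.2.3.

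No size of bias is claimed, and the documents give no basis for one. The direct effect on the patient-reported primary endpoint is limited. The exposure that matters is PI approval of restricted drugs, and withdrawal before the 3-month visit, which changes who is analysed. Adverse-event judgements come second.

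This rests on two assumptions: that the list is readable when the PI receives it, since nothing available says otherwise, and that withdrawal by the investigator or after a code break counts as discontinuing under the 3-month exclusion rule. If the list is in practice sealed or masked, the remaining defect is that the protocol does not say so.

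**What to change.** 1. Amend 10.2.1 so that the third party provides the readable sequence only to an unblinded person with no role in enrolment, assessment or analysis. The research pharmacist who receives unblinded drug under 6.1.1 is one example. State that the PI, other investigators, coordinators and the analyst have no access before data lock.
2. Reconcile 6.1.1, 6.1.3 and 6.1.4 on who receives the drug and who prepares the syringes.
3. Amend 10.2.3 so that a code break reveals one patient's assignment only, from the list holder or from a sealed single-patient code, and is logged. The PI keeps the ability to unblind for care.
4. In 6.2, keep per-subject accountability records that identify the product with the unblinded person until data lock.

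The cost is protocol wording plus either a contact route to the list holder or a set of sealed codes. If the research pharmacist prepares every syringe, no new role is needed. Otherwise one preparer has to be named as unblinded and kept out of enrolment, assessment and analysis. No visits or procedures are added.

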10.2.2 EVALUATION OF SUCCESS OF BLINDING

Not applicable.

10.2.3 BREAKING THE STUDY BLIND/PARTICIPANT CODE

Breaking the randomization code will be performed by the Principal Investigator and will occur if it is necessary for the care of the subjects. For example, if an AE or SAE occurs with the a subject and knowledge of the drug randomization would be important for clinical care or to determine appropriate treatment, then the principal investigator will break the code and the subject will be withdrawn from the study.

Unblinding of a subject(s) dosing will be documented and will include an explanation of why the study medication was unblinded.

Following data lock, subject dosing information can be unblinded and the unblinded information can be sent to the study participants at the discretion of the principal investigator.

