	 Local intolerance of the administered Anakinra (Kineret®) or any sign of allergic response. Development of signs and symptoms before the second time point preventing the second administration of the study drug. Any patient reported and drug related SAE after the first or second administration of the study drug. Diagnosis with any condition as outlined in the exclusion criteria during the course of the initial 2 weeks of study enrollment.
Population:	The study population will include up to 40 subjects within 28 days following of injury. The study is open to male and female participants who are between the ages of 14 and 40, who have ACL tears. Participants will be enrolled at the University of Kentucky.

Phase:	2
Number of Sites enrolling	1 (University of Kentucky)
participants:	
Description of Study	IL-1ra (Kineret®, anakinra), supplied by Sobi Pharmaceuticals, is a
Agent :	recombinant, nonglycosylated form of human interleukin-1 receptor antagonist (IL-1Ra). Kineret® consists of 153 amino acids and has a molecular weight of 17.3 kilodaltons. It is produced by recombinant DNA technology using an E coli bacterial expression system. It is available as pre-filled syringes (100 mg in 0.67 mls) and is FDA approved for daily subcutaneous injection (100 mg/day) for treatment of rheumatoid arthritis (age > 10). A total of 1.5 ml (150 mg) will be injected intra-articularly after synovial fluid aspiration 'to dryness' once between 1 and 28 days after ACL injury.
Study Duration:	24-36 months
Participant	2 years
Duration:	•

SCHEMATIC OF STUDY DESIGN

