2.2 RATIONALE

We hypothesize that IL-1Ra administered intra-articularly during the early phase of acute ACL injury will provide symptomatic pain relief and decrease synovial fluid inflammatory and cartilage degradation markers. ACL injury produces high levels of inflammatory mediators, including as IL-1, which mediate knee pain, perpetuate synovitis, and decrease functional recovery post injury and post-surgically. We have designed a clinical trial that specifically tests the ability of IL-1ra to alleviate pain following acute ACL injury and potentially changes patient reported outcomes at 2 years.

A total of 1 mL (150 mg) will be injected intra-articularly after synovial fluid aspiration 'to dryness' once at study entry 1-28 days after injury depending on time of presentation).

Rational for including pediatric population

The specific reason for enrolling the age group of children aged 14-18 is that these children have a musculoskeletal physiology like adults.

- Their major growth plates are closed.
- These patients may be treated surgically like adult patients with exactly the same surgical preparation, technique and rehabilitation as adults.
- Children, particularly girls, between the ages of 14 and 18 have the highest statistical risk in any population of tearing their Anterior Cruciate Ligament. ^{25,45}
- Children in this age group are particularly vulnerable to the later development of osteoarthritis. Lohmander et al showed that young female soccer players in this age group developed symptomatic knee Osteoarthritis secondary to the ACL injury within 12 years of the injury.²⁴ One could therefore argue that particularly children between completed puberty and 18 years of age have to be the patients requiring most of our concern regarding development of OA.
- *Furman et al.* showed that early post-injury administration of IL-1Ra did not alter bone morphology or fracture healing after intra-articular fracture but significantly reduced cartilage degradation and inflammation.⁽⁴⁶⁾
- The value of intraarticular IL-1 blockade when given immediately after intraarticular injury has been demonstrated repeatedly. In a recent publication of *Genemaras et al.* the early administration of IL-1Ra could be shown to significantly down-regulate proinflammatory Il1-β, TNF-α) and chondrodegredatory markers (MMP-3,ADAMTS-4,ADAMTS-5) immediately after non-destructive chondral impact injury to porcine articular cartilage⁽⁴⁵⁾.

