2.3 POTENTIAL RISKS AND BENEFITS

2.3.1 KNOWN POTENTIAL RISKS

Safety Precautions: Participants will be followed at regular intervals by their study doctor. During each visit participants will be evaluated for adverse events according to GCP guidelines and reported accordingly to IRB and FDA regulations.

Risks associated with Kineret®:

Reproductive Risks: It is not known whether receiving Kineret® is harmful to an unborn child. Pregnancy after administration of Kineret® may involve risks to the mother, and her embryo or fetus. Therefore, females who are capable of reproducing, must use effective contraceptive methods. These methods must be used from the time of screening until Visit 2 during which any remaining medication will be washed out of the joint during the surgery. If the participant does not elect to have surgery (visit 2) contraception methods will be documented until the end of the study. Examples of effective birth control are: hormonal contraceptives (the pill, implant, transdermal patch, or injection), barrier methods (condom with spermicide, diaphragm with spermicide), IUD, or a male partner had a vasectomy.

Lactating women: It is not known whether this drug or its metabolites are excreted in human milk. Because many drugs are excreted in human milk, caution should be exercised when Kineret® is administered to a nursing woman.

Limitations, potential problems, and alternatives: This study will allow for safety and efficacy assessment in patients with acute effusive knee injury.

- Dose: Based on our work and the work of others, we believe 150 mg dosage is appropriate. The goal of the study is to sustain levels of IL-1Ra long enough and a high enough concentrations during the critical, early time period to be effective. For this reason, we have increased our dosage from a single injection (carried out in the preliminary study) to two injections.
- Patient attrition: Close and regular communication, particularly in the intensive first few months, will be provided to all subject participants. Patients will be fully informed of the time commitments and need for a total of three arthrocenteses in order to recruit study subjects willing to participate in the full study. Because arthrocentesis alone can be expected to benefit subjects, education regarding direct and indirect benefits of all aspects of the trial will be provided. Subjects will also receive appropriate compensation for the time and travel.

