6.1.9 DURATION OF THERAPY

Enrolled participants will receive, based on their randomization, either Kineret or a matching saline placebo within 1-28 days after suffering an ACL injury.

If a participant discontinues the study for any reason prior to 3-month visit, then the collected data will be evaluated but not included in the analysis and a replacement participant will be enrolled in the study.

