7.3.2 SCHEDULE OF EVENTS TABLE

This section should capture the procedures that will be accomplished at each study visit and correspond to the descriptions in the above sections.

Procedures	Screening (Visit 1)	Visit 2 ^e	Visit 3	Visit 4	Visit 5	End of Study Visit 6
Time point	1-28 days post injury	Surgery day or 4-6 weeks post injury	4-14 After Visit 2	6 months After Visit 2 (+/- 2 weeks)	12 After Visit 2 (+/- 2 weeks)	24 months After Visit 2 (+/- 4 weeks)
Informed Consent	Х					
Demographics	Х					
Medical history	Х	Х	Х	Х	Х	Х
Randomization	Х					
Administer Investigational Product	Х					
Concurrent meds	Х	Х	Х	Х	Х	Х
Physical Exam	Х					
Range of motion	Х	Х	Х	Х	Х	Х
Vital signs	Х					
Height	Х					
Weight	Х					
Questionnaires	Х	Х		Х	Х	X
Knee Aspiration	Х	Xa	X ^h			
Biomarkers	Х	Х	Х		X ^d	X ^d
Safety Lab Tests ^b	Х					

Procedures	Screening (Visit 1)	Visit 2 ^e	Visit 3	Visit 4	Visit 5	End of Study Visit 6	
Urine pregnancy tests ^c	Х						
Adverse event evaluation	Х	Х	Х	Х	Х	Х	
X-Ray ^f	Х						
MRI ^g	Х				Х	Х	
a: Should a subject be enrolled into the study and choose not to undergo ACL reconstruction aspiration at time of surgery will be omitted. b: Albumin, alkaline phosphatase, total bilirubin, bicarbonate, BUN, calcium, chloride, creatinine, glucose, LDH, phosphorus, potassium, total protein, SGOT [AST], SGPT [ALT], sodium. c: Urine pregnancy test (women of childbearing potential). d: Serum and urine only e. Should a subject be enrolled into the study and choose not to undergo ACL reconstruction, subject will received treatment according to this protocol. For subjects that do not have ACL reconstruction, the time windows will be relative to Visit 2. For example, Visit 3 will be 4-14 days after Visit 2 f. All subjects must have standardized MTP-2 weight bearing x-ray. Documentation of closed growth plates at screening will be noted in the routine SOC x-ray							

g. All subjects enrolled will have an MRI performed regardless if surgery is to be scheduled or not. However, randomization can be performed prior to MRI as the MRI examination is not necessary or required to diagnose the ACL tear.
h. We will only perform the aspiration at Visit 3 if participants had elected to have surgery performed, and if they have fluid on their

knee.

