8.3 TIME PERIOD AND FREQUENCY FOR EVENT ASSESSMENT AND FOLLOW-UP

The occurrence of an AE or SAE may come to the attention of study personnel during study visits and interviews of a study participant presenting for medical care, or upon review by a study monitor. All AEs including local and systemic reactions not meeting the criteria for SAEs will be captured on the appropriate CRF. Information to be collected includes event description, time of onset, clinician's assessment of severity, relationship to study product (assessed only by those with the training and authority to make a diagnosis), and time of resolution/stabilization as well as seriousness of the event. All AEs occurring while on study must be documented appropriately regardless of relationship. All AEs will be followed to adequate resolution.

Any medical condition that is present at the time that the participant is screened will be considered as baseline and not reported as an AE. However, if the study participant's condition deteriorates at any time during the study, it will be recorded as an AE. UPs will be recorded in the data collection system throughout the study.

Changes in the severity of an AE will be documented to allow an assessment of the duration of the event at each level of severity to be performed. AEs characterized as intermittent require documentation of onset and duration of each episode.

The PI will record all reportable events with start dates occurring any time after informed consent is obtained until 7 (for non-serious AEs) or 30 days (for SAEs) after the last day of study participation. At each study visit, the investigator will inquire about the occurrence of AE/SAEs since the last visit. Events will be followed for outcome information until resolution or stabilization.

8.4 **REPORTING PROCEDURES**

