10 STATISTICAL CONSIDERATIONS

10.1 STATISTICAL AND ANALYTICAL PLANS

10.1.1 GENERAL APPROACH

Sample Size and Power Analysis - The primary outcome aim of the study is to determine if treatment with the study medication results in greater improvements in patient-reported outcomes one year following surgery. We will use the validated Knee Osteoarthritis and injury Outcome Score (KOOS),[27] which is a self-administered, knee-specific instrument that evaluates the course of knee injury and treatment outcomes. To reduce the risk of an underpowered RCT, an a priori sample size estimation was calculated from data collected from recent studies of ACL-injured and -reconstructed patients.[28-32] The previously published oneyear KOOS Quality of Life Scores are 60.2 ± 24.2 [31] and the minimal detectable change of this instrument is 7.2 [32]. Assuming that the standard deviation of the change scores between the day of surgery and one year postoperative visits will be 20% of the standard deviation of the standard deviation of the one-year KOOS Quality of Life Scores ($.2 \times 24.2 = 4.8$), a sample size of 16 patients per group (32total) would be at least 80% powered to detect a difference of 7.2 points between the treatment group and the control group (One-way ANOVA model with alpha = 0.05, Effect size = 7.2/4.8 = 1.5, G*Power 3.0.10). This sample size would adequately power the study for the primary outcome variable, but would also adequately power the study for the second aim of the study. The second aim of the study is to compare chondrodegenerative biomarkers between groups at the 1 year follow up. We have previously observed large effect sizes between groups in preliminary studies (ES = 1.34), and a sample size of 32 patients (16 per group) would be at least 80% powered to detect effect sizes of this magnitude. However, to protect against an underpowered study due to patient attrition, we will monitor compliance and potentially enroll up to 20 patients per group in order to adjust for attrition. Patient costs will not occur until sample or MRI analysis.

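### Breaking the code for an adverse event automatically withdraws the subject from the study, so later outcome and new-event data are lost for a reason that may depend on treatment

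*Combined protocol and SAP*

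**What the plan says.** Section 10.2.3 allows the principal investigator to break the code when a subject's care needs it. Its example is an AE or SAE for which the allocation bears on care or choice of treatment, and there "then the principal investigator will break the code and the subject will be withdrawn from the study". The withdrawal is from the study, not only from study drug, and no exception is given.

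On dosing, the Protocol Summary has the injection given "once between 1 and 28 days after ACL injury" and section 2.2 has it "once at study entry 1-28 days after injury depending on time of presentation". Sections 4.1 and 6.1.5 describe one injection per group. Section 6.1.9 has subjects receive "either Kineret or a matching saline placebo within 1-28 days after suffering an ACL injury". In the section 7.3.2 table the row "Administer Investigational Product" is marked at Visit 1 only. Other text differs. Section 2.3.1 says "we have increased our dosage from a single injection (carried out in the preliminary study) to two injections", the stopping criteria (Protocol Summary, 8.5 and 10.1.2) mention a second administration, and section 7.3.1 calls the Visit 1 injection a first dose.

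On follow-up, section 8.3 records reportable events "until 7 (for non-serious AEs) or 30 days (for SAEs) after the last day of study participation". Events already recorded are followed to resolution or stabilisation (8.3, 8.4.1, 8.4.2). For a subject who leaves, section 5.4.2 collects the reason and says nothing of further visits. Sections 5.4.2, 6.1.9 and 10.2.1 leave out of the analysis, and replace, anyone who discontinues before a 3-month visit.

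**The concern.** Unblinding answers a question about one patient's care. Leaving the study answers a different question: whether data collection should stop. Section 10.2.3 joins the two, so a code break also ends the subject's scheduled assessments.

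The trigger occurs after randomisation and may be related to the assigned treatment, so the resulting missing data are not plausibly random. Section 10.1.1 names no method for missing data that could address this. In a phase 2 trial of at most 40 people, some of them minors, both the KOOS comparison and the later safety record would be thinner in patients whose events made the allocation relevant.

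**Working it through.** The plan states no figure on this point, so the check is mainly a comparison of its sections.

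**1. Does withdrawal limit exposure?** On the single-injection text (Protocol Summary, 2.2, 4.1, 6.1.5, 7.3.2), dosing is complete once Visit 1 is over, so withdrawal stops no further drug. On the two-dose text (2.3.1 and the stopping criteria), a code break between doses could coincide with an end of dosing, but that still would not require an end to visits. The point therefore does not depend on how the dosing text is reconciled. Nor is automatic withdrawal needed as protection, because section 5.4.1 already lets the investigator end participation when continuing is not in the subject's interest.

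**2. What is lost?** From sections 7.3.1 and 7.3.2, with no section providing for visits after withdrawal:

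| Withdrawn | KOOS lost at | MRI lost at | Biomarkers lost at |
|---|---|---|---|
| Between Visits 1 and 2 | Visits 2, 4, 5, 6 | Visits 5, 6 | Visits 2, 3, 5, 6 |
| Between Visits 3 and 4 | Visits 4, 5, 6 | Visits 5, 6 | Visits 5, 6 |
| Between Visits 4 and 5 | Visits 5, 6 | Visits 5, 6 | Visits 5, 6 |
| Between Visits 5 and 6 | Visit 6 | Visit 6 | Visit 6 |

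Range of motion and the scheduled AE review are lost at every remaining visit.

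**3. How long are new events recorded?** Last recording day = day of withdrawal + 7 (non-serious) or + 30 (serious). For an assumed withdrawal on day 14 after injection:
- non-serious: 14 + 7 = day 21
- serious: 14 + 30 = day 44
- subject who stays: Visit 6 is 24 months (about 730 days) after Visit 2. If Visit 2 falls 0 to 6 weeks after injection (assumed), that is 730 + 0 = 730 to 730 + 42 = 772 days.

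**4. Link to the replacement rule.** A code break before the 3-month visit becomes a discontinuation under 10.2.3 and then an exclusion and replacement under 5.4.2, 6.1.9 and 10.2.1. The schedule has no 3-month visit, so the cut-off is not tied to an assessment. After the cut-off, the subject is withdrawn without replacement.

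**5. Size.** One subject is 1/20 = 5% of an arm. The documents give no expected number of code breaks, so what follows is a scenario, not a forecast. Suppose k of 20 subjects in one arm are withdrawn without replacement and would have scored D points worse than the rest. The mean of those remaining then overstates the arm mean by (k/20) × D. For D, I take the two KOOS figures in section 10.1.1, both for the Quality of Life subscale: the 7.2-point target difference and the standard deviation of 24.2.

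| k | D = 7.2 | D = 24.2 |
|---|---|---|
| 1 | 0.36 | 1.21 |
| 2 | 0.72 | 2.42 |
| 3 | 1.08 | 3.63 |

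Against the 7.2-point target, this runs from 0.36/7.2 = 5% to 3.63/7.2 = 50%.

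**The case against.** The strongest reply is that the rule adds little. The plan describes the drug as having a short half-life in vivo (2.1, 2.3.2), so the allocation will seldom matter for care months later. Code breaks are likeliest early, when the exclude-and-replace rule already removes the subject from the analysis. The triggering event is still followed. Section 8.4.1 also speaks of toxicity follow-up for 30 days after treatment is discontinued, which makes the contrast with two years less sharp. Power on the plan's inputs is not at risk: with effect size 7.2/4.8 = 1.5 and two-sided alpha 0.05, 16 per group gives power 0.984 by t-test, and 9 per group suffice for 80%.

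Much of this stands as a limit on size. It does not remove the defect. Section 10.2.3 applies throughout follow-up and, early on, is itself a route into the exclusion. Section 8.3 and the schedule collect new events through Visit 6 in everyone who stays. Bias from selective loss is not cured by spare power.

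A reader might infer more than the documents support:
- *That follow-up is cut short in exactly the patients with the most important events.* The trigger is that allocation matters for care, which overlaps with seriousness but is not the same.
- *That each unblinded subject uses a quarter of the attrition allowance.* Section 10.1.1 may "potentially enroll up to 20 patients per group in order to adjust for attrition", which is 20 − 16 = 4 per arm, but subjects who leave before the 3-month visit are replaced and do not draw on it.
- *That the loss falls in the arm with more events.* No section says which arm that would be, and the earlier intra-articular anakinra studies described in 2.1 and 2.2 reported no significant adverse events.

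**Conclusion.** The point holds in a limited form. Section 10.2.3 turns a code break for an AE or SAE into automatic withdrawal from the study. No section then provides for further visits, so later KOOS, range-of-motion, biomarker and MRI data are lost, and new-event recording closes after 7 or 30 days. The triggering event itself is not lost.

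The loss can bias the comparison because its cause arises after randomisation and may relate to treatment. Its direction and size are unknown. The 5% share is arithmetic, while the shifts of 0.36 to 3.63 points rest on assumed values of k and D. The conclusion does not depend on whether one or two doses are intended, but the sections that disagree on this must be reconciled.

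**What to change.** In section 10.2.3, replace the withdrawal clause with:

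> Unblinding does not by itself end study participation. Unless consent is withdrawn or the investigator ends participation under 5.4.1, the subject continues the scheduled safety assessments, questionnaires and other visits through Visit 6 and is analysed in the assigned group.

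Report the number unblinded by arm, and add a sensitivity analysis that omits KOOS scores obtained after unblinding. With this wording a code break no longer triggers the exclude-and-replace rule by itself. The decision to unblind and the subject's care are unchanged. Separately, reconcile the one-dose and two-dose text.

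The drafting cost is one clause and one analysis. The retained visits are already in the schedule, but the documents contain no budget, so their expense cannot be judged from them. The scientific cost is that some later KOOS self-reports may come from subjects who know their arm. The principal investigator, who breaks the code and also assesses AEs and their expectedness (8.4.1, 8.2.3), will make later assessments in those subjects unblinded. The sensitivity analysis addresses the first; the second should be disclosed when safety is reported.
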